No sub-segment of the population will be specifically excluded from participation in nutrition assessment surveys in emergency-affected populations; however, some population subsegments may not be specifically chosen for inclusion. Women and children are at greater risk of most nutritional deficiencies; therefore, they will be targeted for most nutrition assessment surveys. Men are at substantially lower risk of many nutritional deficiencies and are therefore specifically not targeted for most nutritional assessments. One exception is the assessment of the causes of anemia. Men are often included in such surveys because they are much less susceptible to iron deficiency. Therefore, survey findings indicating that anemia is common among women and children but rare among men provide evidence that iron deficiency is a predominant cause of anemia.

Estimated number of participants

The specific sample size in each nutrition assessment survey depends on many assumptions and factors which may differ from one survey to the next. Commonly, such surveys include 200 - 700 households and all eligible members of target groups who live therein.

Sampling, including sample size and statistical power

The required sample size will be calculated separately for each assessment survey. All sample size calculations use the following assumptions:

- 1) The limit of statistical significance (alpha) = 0.05
- 2) The power (beta) = 0.8

The other assumptions required for sample size calculation will be decided based on the specific population to be assessed. These assumptions include:

- 1) Prevalence of nutritional condition of interest
- 2) Desired precision of point estimate of prevalence, cumulative prevalence, incidence, or mean.
- 3) Population size, if less than 10,000.
- 4) Design effect, if cluster sampling is planned.

The table below shows examples of nutrition conditions of interest, the assumptions used, and the sample size needed which may be used in nutrition assessment surveys in emergency-affected populations. These examples assume a population size greater than 10,000. Of course, the assumptions used and therefore the required sample sizes will differ depending on the nutrition conditions and specific population to be assessed.

Target group and type of malnutrition	Assumed current value	Precision required	DEFF assumed	Sample size needed
Children 6-59 months				
Wasting (< -2 SD)	20%	" 5%	2	492
Stunting (< -2 SD)	50%	" 10%	2	193

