The sampling procedures used will depend on the type of data available for the population. In many displaced populations located in stable camps, an international organization, such as UNHCR, has carried out a complete or near complete census of all camp residents. This registration database supplies a complete list of all households or individuals living in the camp. In these situations, lists of households or target individuals can be generated from which to choose a sample by simple or systematic random sampling. For example, a recent anemia survey in two camps in western Tanzania assessed the prevalence of anemia in children 6-59 months of age and their mothers. It also assessed the prevalence of iron overload in adult men 30 years of age or older. In these two camps, a registration had taken place 9 months prior to the surveys, and the registration database was constantly updated to account for new arrivals and departures. As a result, the registration data provided an excellent sampling frame. Two lists were generated from the database: one of households and one of men 30 years of age or older. A systematic random sample was drawn from the household list after calculation of the required sample size. Households on the household list were visited in order to identify children 6-59 months of age and their mothers to be included in the survey. The basic sampling unit was household while the unit of analysis for nutrition variables was the individual household member. A second sample of men 30 years of age and older was selected by sysematic random sampling from the list of men. Selected men were then recruited for the survey. In this case, both the unit of sampling and unit of analysis was individual men.

In many situations, especially during acute emergencies and new settlements of displaced persons, lists of all households or individuals in the population are not available. In such cases,

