At least one health worker on each survey team is trained to collect the biologic specimens necessary for that specific survey. Such training may include the use of the Hemocue® hemoglobinometer to measure hemoglobin concentration and use of other portable laboratory instruments to be used by survey team members in the field. Fingerstick and phlebotomy technique is reviewed and practiced on other survey team members. Although fingerstick may be taught to naïve survey team members, phlebotomy is done only by health workers already experienced in this technique. The processing and storage of specimens is also taught during the training period and closely supervised during the first days of the survey.

Data handling and analysis

Data analysis plan, including statistical methodology and planned tables and figures

The sampling methods have been previously described (see section "Sampling, including sample size and statistical power" above). Data collection procedures are described in the next section "Data collection").

In general, data analysis includes calculation of proportions to derive the prevalence of various nutrition and health conditions and mean averages of various continuous measurements. Although all possible analyses cannot be determined for all possible nutrition assessment surveys in emergency-affected populations, the example of hemoglobin will illustrate the potential types of data analysis.

An estimate of the importance of anemia among children, women, and men is generated by calculating the proportion of the survey participants for whom hemoglobin concentration falls below the WHO-recommended threshold for defining anemia (see section "Case definitions" above). In addition, survey coordinators graph the distribution of hemoglobin concentrations and calculate the mean hemoglobin concentration for each of the target groups. The statistical precision of all prevalence estimates is assessed using 95% confidence limits, and the statistical significance if differences between subgroups is assessed using Chi square.

Data collection

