malnutrition is assessed in children and adults, the feet and lower legs must be examined for edema to rule out edematous malnutrition which invalidates those anthropometric indices which include weight. Such examination will be done by qualified medical personnel and be as noninvasive as possible. In many children, some measure of mild restraint is required for certain portions of such examinations. Such restraint is minimized and carried out only with parents' permission or by parents themselves.

Collection of biologic specimens. For most micronutrients, clinical manifestations appear late in the deficiency and only among those persons with severe deficiency. As a result, clinical findings almost always underestimate the prevalence of the micronutrient deficiency. For this reason, many nutrition assessment surveys include the collection of biologic specimens in order to obtain more accurate estimates of the prevalence rates and severity of deficiencies of specific micronutrients. The most common micronutrient deficiencies assessed include iron and vitamin A; however, others may be included in specific surveys. The type of specimens, the methods of obtaining the specimen, and target groups for the laboratory assessment of specific micronutrient deficiencies in emergency-affected populations are shown below.

Micronutrient	Specimen	Methods of collection	Common target groups
Iron	Blood	Fingerstick or	Children < 5 years of age
IIOII	Diood	Phlebotomy	Adult women
		Fingerstick or	Children < 5 years of age
Vitamin A	Blood	Phlabotomy	Adult women
		rinebotoniy	Adolescents
P vitamina	Plood	Phlahotomy	Children < 5 years of age
D vitaliilis	Blood	rmebotomy	Adolescents
Vitamin D	Blood	Phlebotomy	Children < 5 years of age
Vitamin C	Blood	Phlebotomy	All ages and sexes
Iodine	Urine	Voluntary urination	Children 8-11 years of age

Information management and analysis software

In most cases, initial data entry and analysis for nutrition assessment surveys in emergency-affected populations will be done using EpiInfo software. In cases where the final report must await the results of laboratory results, the final data analysis can be done using SAS or SUDAAN.

Data entry, editing and management, including handling of data collection forms, different versions of data, and data storage and disposition

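### In cluster surveys the sample size allows for clustering, but the analysis section names Chi square and 95% confidence limits without requiring either to do so

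*Protocol*

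**What the plan says.** **Sampling.** The Protocol section *Sampling, including sample size and statistical power* describes two situations. Where a camp registration list exists, households or individuals are drawn from it directly. Where no list exists, cluster or multi-stage sampling is required. The Afghanistan example took 30 villages with probability proportional to size, and included all target-group members of each sampled household.

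**Sample size.** The planning inputs include "Design effect, if cluster sampling is planned". All six rows of the example table use a DEFF of 2, and the text below it reports 1.5 for the Afghanistan survey. The same section says that equal-probability selection makes weighting unnecessary. It draws no other consequence for the analysis.

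**Analysis.** The section *Data analysis plan, including statistical methodology and planned tables and figures* uses hemoglobin as its worked example. It assesses the precision of all prevalence estimates by 95% confidence limits and says that "statistical significance if differences between subgroups is assessed using Chi square". It refers back to the sampling section but does not mention clustering, the design effect or a design-based variance.

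**Software.** Under *Information management and analysis software*, initial analysis is usually in EpiInfo. Where the report has to wait for laboratory results, "the final data analysis can be done using SAS or SUDAAN". No procedure is named for any package.

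**The concern.** The standard Chi square treats individuals as independent. The sample size table assumes that they are not. The plan therefore pays for clustering when it sets the number of participants, but does not require it to be carried into the tests and limits. Equal selection probabilities remove the need for weights; they do not remove the correlation between people in the same village.

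Two uses of the results are exposed. *Study design and locations* gives the identification of vulnerable subgroups as a possible use, and a test that rejects too often would flag differences between areas that are only cluster-to-cluster variation. *Intended and potential use of the findings* says that the prevalence of acute malnutrition largely decides the type of feeding programme, and limits computed without the design would make that prevalence look more precise than it is.

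**Working it through.** **Inputs from the Protocol** (sampling section): alpha 0.05, taken as two-sided because z = 1.96 reproduces the table; DEFF 2 in the examples and 1.5 in the Afghanistan survey; prevalence and precision of 20% ± 5 points (wasting), 50% ± 10 (stunting) and 10% ± 5 (anemia in men).

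**1. Reproduce the plan's sample sizes.** N = DEFF × 1.96² × p(1 − p) / d², rounded up:

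- Wasting: 2 × 3.8415 × 0.16 / 0.0025 = 491.7, so 492 (stated 492).
- Stunting: 2 × 3.8415 × 0.25 / 0.01 = 192.1, so 193 (stated 193).
- Anemia in men: 2 × 3.8415 × 0.09 / 0.0025 = 276.6, so 277 (stated 277).

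All three match. The table is a precision calculation in which the variance is doubled for clustering.

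**2. True size of an uncorrected 1-df Chi square.** If the variance of the contrast is DEFF times what the test assumes, size = 2 × [1 − Φ(1.96/√DEFF)], and an uncorrected 95% interval covers 1 minus the same quantity, with DEFF now that of the estimate.

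| DEFF | 1.96/√DEFF | True size of 5% test | Coverage of uncorrected 95% limits |
|---|---|---|---|
| 1.5 | 1.600 | 11.0% | 89.0% |
| 2 | 1.386 | 16.6% | 83.4% |
| 3 (not in the Protocol; for range) | 1.132 | 25.8% | 74.2% |

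**3. Reported precision for wasting, n = 492, p = 0.20.**

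- Ignoring the design: 1.96 × √(0.16/492) = 3.53 points.
- With DEFF 2: 3.53 × √2 = 5.00 points, the precision that the table was built to deliver.

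**4. Which contrasts are affected.** A beta-binomial simulation (20,000 runs, 30 clusters of 16 or 20 persons, prevalence 20% or 50%, intracluster correlation set to give DEFF 2; cluster size and correlation are assumptions) gave:

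- Subgroups made of whole clusters: the uncorrected test rejects in 16.2% to 16.7% of runs.
- Subgroups split evenly inside every cluster, as sex would be: 4.1% to 4.4%.
- Overall prevalence: uncorrected limits cover 83% to 84%.

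A second simulation (30 clusters, about 495 children, one or two per household, overall DEFF about 2, and a household share of the latent variance from 0 to 0.3, all assumed) gave 15% to 16% for whole-cluster subgroups. Subgroups of whole households scattered across clusters gave roughly 4% to 6%. The cluster effect largely cancels when both subgroups occur in every cluster. A household trait that itself follows village lines, as water source might, would fall in between.

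**The case against.** **The protocol is silent on variance; it does not prescribe a wrong one.** This is an umbrella protocol, its analysis section is illustrative, and variance estimation is commonly left to an analysis plan that is not shown here. This stands for the confidence limits: nothing says that they ignore the design, so the coverage figures are conditional. It stands less well for the test. The section sets out statistical methodology, names Chi square for subgroup differences, and gives no qualification for the cluster surveys that the same document requires.

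**The software can do the right analysis.** SUDAAN is listed, so a design-based analysis is possible. But it is optional and is mentioned only for reports that wait for laboratory results. Under *Disseminating results to public*, anthropometry, hemoglobin and vaccination coverage often go into an earlier preliminary report.

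**The surveys are descriptive.** *Hypothesis or questions* states that there are no a priori hypotheses, and subgroup comparison is a secondary use. This stands and lowers the severity.

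**A stronger reading is tempting.** A reader might infer that every subgroup test in these surveys runs at 17% and that every interval covers 83%. The documents do not support that:

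- Camps with registration lists are not cluster-sampled, and in the Tanzania example the men were sampled and analysed as individuals.
- DEFF 2 belongs to worked examples, and the one actual survey with a stated value used 1.5.
- The 17% applies to contrasts along cluster lines, not to sex or to household groups spread across clusters.

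A reader might also infer that list-based household samples are seriously affected, because there "The basic sampling unit was household while the unit of analysis for nutrition variables was the individual household member". Households with several eligible members are indeed small clusters. The size of that effect depends on members per household and within-household correlation, and the Protocol gives neither. Assuming 1.5 children per household and a correlation of 0.3, DEFF is 1 + 0.5 × 0.3 = 1.15. The test size is then 6.8%, falling to 5% as the correlation goes to zero.

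**Conclusion.** The point holds for surveys that use cluster or multi-stage sampling. There the sample size reflects the design, and the named test and limits are not required to.

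- **Tests:** if the standard Chi square is used on subgroups that follow cluster lines, a nominal 5% test has a true size of about 17% at DEFF 2 and 11% at DEFF 1.5. These are not ceilings if the actual design effect is larger. Subgroups spread within clusters show little or no inflation.
- **Limits:** if they are also computed without the design, coverage is about 83% or 89%, and the wasting half-width would be given as 3.5 points when the design delivers 5.0.

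The test figures assume that the DEFF of the contrast equals the planning value. The coverage figures assume an analysis that the Protocol neither states nor excludes. Severity is moderate: the surveys are descriptive, the sample sizes themselves are sound, and the repair needs no new data.

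**What to change.** Add to the data analysis plan section, in words such as these: *In surveys with cluster or multi-stage sampling, all confidence limits and subgroup tests, in preliminary and final reports, use design-based variances with the primary sampling unit as the cluster: Taylor linearisation for proportions and means, and a Rao-Scott chi-square or F test for subgroup comparisons. The observed design effect is reported for each outcome. In list-based household samples with more than one eligible member per household, the household is the cluster.*

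The design-effect item in the planning list need not change. The household effect is likely to be small, and the Protocol gives no figures from which to size it.

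**Cost.** Wording only. The example data collection form in Appendix 1 already records cluster and household numbers, so no extra fieldwork or sample is needed. Compared with an analysis that ignores the design, intervals will be wider and there is slightly more analysis work. In return, the reported precision matches what the sample size was planned to give, and the observed design effects can inform later surveys.

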As described above, the type, extent, and urgency of food and nutrition interventions will depend on the findings of a nutrition assessment survey in an emergency-affected population. Such interventions could include:

- 1) Distribution of relief food to the entire population as an emergency general ration.
- 2) Supplementary feeding provided to persons with moderate protein-energy malnutrition, as identified by screening.
- 3) Supplementary feeding provided to all persons in specified vulnerable groups, e.g. children less than 5 years of age or pregnant and lactating women.
- 4) Therapeutic feeding of persons identified with severe protein-energy malnutrition.
- 5) Specific therapy for persons identified with certain micronutrient deficiencies, e.g. provision of iron tablets to children with pallor or provision of vitamin A to children with Bitots spots.

- 6) Targeted supplementation of groups identified by screening as having a specific micronutrient deficiency, e.g. iron supplementation of pregnant women or young children.
- 7) Distribution of fortified food in the general ration or supplementary feeding program, e.g. inclusion of fortified corn-soy blend cereal in relief rations.

Disseminating results to public

The results of nutrition assessment surveys are presented in written reports distributed widely to all concerned organizations and agencies. Most sponsoring agencies also post these reports on websites or widely disseminate them electronically to other interested persons. Often a preliminary report contains those results available immediately after data collection, including answers to interview questions, anthropometric assessment, hemoglobin measurements, and an estimate of vaccination coverage among children. This preliminary report is often discussed in a consultative meeting with all participating organizations.

Dissemination of results may also include verbal presentations in the location where the survey was done, as well as regional and national capital cities and the headquarters of the sponsoring organization. During such debriefings, survey coordinators are available to answer questions during these presentations.

In those surveys in which testing is done in a remote laboratory, a second final report is drafted by survey coordinators when these laboratory results become available. This report includes specific recommendations not included in the preliminary report which may be based on the new laboratory results. Survey results may also be published in the biomedical literature. As described above, authors of such publications must obtain clearance from all organizations sponsoring these survey.

SUPPLEMENTAL INFORMATION FOR PROTECTION OF HUMAN RESEARCH PARTICIPANTS

In general, nutrition assessment surveys performed in emergency-affected populations do not fit the definition of research. The goal of such surveys is the evaluation of the nutrition and health status of a specific population at a specific point in time. Although the methods and results of specific surveys may occassionally be useful to guide future assessment surveys, the production of generalizable scientific knowledge is not a major goal of such surveys. Nonetheless, nutrition assessment surveys are sometimes published in the biomedical literature because they produce lessons which may assist other relief workers in performing similar future assessments. Regardless, the risks and benefits of survey participation are presented below.

Description of risks (physical, social, psychological) to the individual or group. Include methods to minimize risks

The physical risks of participation in nutrition assessment surveys include only those of fingerstick and phlebotomy. Both procedures involve some discomfort. Possible adverse outcomes from these procedures are discussed above (see section "Identifying, managing, and reporting adverse events"). As mentioned previously, survey personnel will monitor participants for some minutes after these procedures to ensure that bleeding has stopped and no syncope occurs.

Social and psychological risks are minimal. No sensitive questions will be asked during interviews. Although in many populations, privacy is difficult to achieve during data collection, all possible efforts will be made to keep participants responses and findings as private as possible. No survey data will ever be connected to identifying information in a report, manuscript, or verbal debriefing.

Description of anticipated benefits to the research participant

As mentioned above, participants will learn the results of some laboratory testing and physical examination and may benefit from referral or immediate treatment. In addition, indirect benefits to survey participants include the benefits accrued to the entire population as a result of the interventions based on the survey findings.

Description of the potential risks to anticipated benefit ratio

The risk of participation includes only the minimal risk of fingerstick and, in some surveys, phlebotomy. The benefit includes the implementation of critical food and nutrition programs in population with potentially serious nutritional deficiencies.

Justification for involving vulnerable participant populations

Protein-energy malnutrition and most micronutrient deficiencies occur in vulnerable populations, such as young children, women of child-bearing age, and pregnant and lactating women. As a result, assessment of these problems must be directed to these vulnerable populations to achieve the maximum likelihood of detecting these conditions if they are present in an emergency-affected population.

Procedures for implementing and documenting informed consent

As described above, prior to enrollment, verbal consent will be obtained from all adults and from parents or caretakers of children selected for participation in the survey. The explanation of the survey will include the purpose of the survey, the types of questions which will be asked, the procedure for weighing and measuring children 6-59 months of age and women of childbearing age, procedures for examining children and women, and a description of the type and quantity of biologic specimens to be obtained as well as the procedures necessary for specimen collection. The granting of verbal consent will be indicated on the data collection form. Written consent is not practical in most nutrition assessment surveys in emergency-affected populations because the majority of survey participants in many populations are illiterate, the risks to survey participants is very small, and the time necessary for extensive explanation of all facets of the survey is not available.

Survey team members will advise survey coordinators regarding the culturally most appropriate way to explain the survey and obtain verbal consent. Survey coordinators, in collaboration with survey team members, may produce a list of items to be covered when seeking consent. An example of such a list is contained in Appendix 2.

Justification for waiver of documentation of informed consent

As described above, the risk attendant to participation in nutrition assessment surveys in emergency-affected populations is very minimal. Written consent is not required in the United States nor in most countries of the world for the procedures (fingerstick and phlebotomy for nutritional assessment, physical examination, and response to questionnaire questions) used in such surveys. Moreover, requiring written consent would make nutrition assessment surveys impossible in many emergency-affected populations because a majority of the members of many such populations cannot write nor sign their name.

Description of procedures for implementing and documenting the assent process of children

Because the children included in most nutrition assessment surveys are less than 5 years of age, assent is not required. Consent will be obtained from the mothers or guardians of all children, regardless of age. In those surveys which assess the extent of iodine deficiency by testing urine of children 8-11 years of age, assent will be sought from these children for collection of urine specimens.

Description of procedures for implementing and documenting parents' or guardians' permission

The data collection form used in most nutrition assessment surveys provides a space for survey team members to record the verbal consent of an adult household member for participation of all household members in the data collection procedures. Separate consent for each household member's participation is obtained, but not recorded on the data collection form.

Provisions for protecting privacy/confidentiality

As mentioned above, the paper data collection forms completed in the field will not contain identifying information. As a result, the computer dataset resulting from data entry of these forms will also not contain any identifying information. Data collection forms and laboratory specimens are matched by recording on both forms and specimens a numeric code number which is specific for each household and individual participant. In most surveys, a sample list is

created when the final selection of households or individuals is made during the sampling process. In cluster surveys, there is a separate form for each cluster, often called a cluster control form, which lists all the households or individuals selected for that cluster. These sample lists and cluster control forms will contain both identifying information and the numeric code described above, and thus can serve as a key to match the code numbers to specific individual participants. This key is necessary to follow-up with specific survey participants if necessary. At the end of the survey, these sample lists will be destroyed or permanently stored separate from the paper data collection forms. Only authorized survey coordinators will have access to the sample lists and data collection forms. Final deposition of all paper and electronic survey materials, including computer datasets and paper forms, will be determined by the organization or agency which funds the survey. In most cases, the sample lists and paper data collection will not return to Atlanta with IERHB personnel.

APPENDIX 1

Nutrition and Health Survey, Afghanistan, 2002

Province	District	Village)	
Cluster number:	_Household number:			
Team code:	Interviewer code:	Date of interview:	/	
			Day	Month

HOUSEHOLD DATA

1)	Does your family now live in your usual place of residence? (circle one)	Yes	/ N o / U nk
	1a) If NO, how long since the family has lived there?	months OR	years
2)	Has anyone in the family received any relief food since the change in government?.	Yes /	No / Unk
3)	What is your main source of water? (circle one)Central piped system /	Truck or water seller	r / Bore hole
	Open W ell / R iver	or stream / Lake or p	ond / Other
4)	Do you use the same source of water now as you did this time last year?	Yes /	No / Unk
5)	How long does it take you to fetch water each time you go to get it?	······	minutes
6)	Results of iodine testing of salt used for last night's food (circle one)I	Positive / Negative	/ Not Done

I would like to ask you about each person who **lived in this household at the time of Eid Qurban 1379** (2001 Gregorian calendar) and children who were born since the time of Eid Qurban:

HOUS Head of on	EHOL house 1 st line	D MEMBI	ERS 1. 2. 3. 4.	Alive (livin Alive (livin Died Missing/L	ng in this ho ng elsewho Jnknown	ousehold) ere)	When was he/she did he/she h feet or leas	became ill, very thin or nave swollen	was she pregnant or at the time of Chil or Nefaz?
	Per son no.	Age (years)	Sex (circle one)	Curren as of T (circl	nt Status TODAY le one)	If missing or dead, since when? (mm/yy)	Died of which cause? (ask questions)	Walnutrition?	Pregnant or in Chel??
\vdash	1		M / F	1 2	3 4	/		Y / N	Y / N
	2		M / F	1 2	3 4	/		Y / N	Y / N
	3		M / F	1 2	3 4	/		Y / N	Y / N
	4		M / F	1 2	3 4	/		Y / N	Y / N
	5		M / F	1 2	3 4	/		Y / N	Y / N
	6		M / F	1 2	3 4	/		Y / N	Y / N
	7		M / F	1 2	3 4	/		Y / N	Y / N
	8		M / F	1 2	3 4	/		Y / N	Y / N
	9		M / F	1 2	3 4	/		Y / N	Y / N
	10		M / F	1 2	3 4	/		Y / N	Y / N
	11		M / F	1 2	3 4	/		Y / N	Y / N
	12		M / F	1 2	3 4	/		Y / N	Y / N
	13		M / F	1 2	3 4	/		Y / N	Y / N
	14		M / F	1 2	3 4	/		Y / N	Y / N
	15		M / F	1 2	3 4	/		Y / N	Y / N

LIVING WOMEN OF CHILDBEARING AGE (15 – 49 years)

Person no. from table 1 above.	Literate ?	Night blind- ness	Goiter	Preg- nant now?	No. of doses tetanus vaccine	MUAC (cms)	Weight (kgs)	Height (cms)	Hemoglobin (gms)
	Y/N	Y / N	Y / N	Y / N				,,,	
	Y/N	Y / N	Y / N	Y / N				,,	, ,
	Y/N	Y / N	Y / N	Y / N		,	,	,,	, ,
	Y/N	Y / N	Y / N	Y / N		,,	,	,,	,,
	Y/N	Y / N	Y / N	Y / N		,,	,	,,	,,
	Y/N	Y / N	Y / N	Y / N		,	,	,,	,,
	Y/N	Y / N	Y / N	Y / N		,	,	,,	,,
	Y/N	Y / N	Y / N	Y / N		,	,	,,	,,
	Y/N	Y / N	Y / N	Y / N		,	,	,	,
	Y/N	Y / N	Y / N	Y / N					

Clus	ster number:	HH:	_ Child's person number:	Mot	ner's pers	son number:				
Que	stions for adult ca	retaker								
1) F	Relationship of res	pondent to ch	ild:	. Mother	Father	Grandmothe	er Grand	dfathe	r O	ther
2) I	s this child's mothe	er alive?					.Yes	/ N o	/	Unk
3) 5	Sex						M a	le /	Fer	nale
4) [Date of birth OR Ag	ge in months.			/	/	OR _		mo	nths
				[Day Mo	onth Year.				
5) [Does this child hav	e difficulty see	eing at night or in the evenin	g when ot	her peop	ole do not?	Yes	N o	/	Unk
6) 5	Since this time yes	terday, has th	is child breast fed?				Yes /	N o	/	Unk
	6a) If YES, was	breast milk th	is child's main source of foo	d since ye	sterday?		Yes ,	/ N o	/	U nk
	6b) If YES, how	long after birt	h did this child first breastfee	ed?			······		_ h	ours
7) \$	Since this time yes (circle all that are)	terday, has th true) P	is child received anything ot owered milk or infant formul	her than b a / S emi-	reast mil solid or s	lk? solid food / No	Water, one of t	tea, c hese	or ju	ice /
8) \$	Since this time yes	teday, has thi	s child drunk anything from a	a bottle wi	th a nipp	le?	.Yes	/ N o	/	Unk
9) H	Has this child recei (show example)	ved any vitar	in A? Vitamin A is given as	drops fron	n a capsi	ule	Yes	N o	/	U nk
10)	Since 2 weeks ago	o, has this chi	d had diarrhea? Diarrhea is	3 or more	e stools i	n 24 hours	.Yes	/ N o	/	Unk
	10a) If YES, was	s this child tak	en to a clinic or hospital for	this proble	em?		.Yes	/ N o	/	Unk
11)	Since two weeks a	ago, has this c	hild had fever and difficulty	breathing	·		.Yes	/ N o	/	Unk
	10a) If YES, was	s this child tak	en to a clinic or hospital for	this proble	em?		.Yes	/ N o	/	Unk
12)	Since the change This vaccine is g	of governmen given by inject	t, has this child received me ion.	asles vac	cination?		.Yes	/ N o	/	U nk
Exa	mination of child									
13)	Bitot's spots							Yes	/	No
14)	Gums bleeding sp	ontaneously.						Yes	/	Νο
15)	Gums bleed upon	tapping						Yes	/	Νο
16)	Angular stomatitis						······	Yes	/	Νο
17)	Pallor in palms of I	hands						Yes	/	No
18)	BCG scar							Yes	/	No
19)	Row of ricketts							Yes	/	No
20)	Perifollicular hemo	orrhage						Yes	/	No
21)	Swollen joints – so	oft and painful						Yes	/	Νο
22)	Swollen joints – ha	ard and not pa	inful					Yes	/	Νο
23)	Bruises or eccymo	sis on legs						Yes	/	No
24)	Bowed legs							Yes	/	No
25)	Bilateral edema							Yes	/	No
26)	Spinal deformity							Yes	/	No
27)	Does this child hav	ve a physical	deformity making it difficult to	o obtain a	n accura	te height?		Yes	/	No
Anth	propometry and lat	poratory								
28)	Weight: (kgs)							,	·	
29)	Length/Height: (cn	ns)						,		
30)	MUAC: (cms)									
31)	Hemoglobin:
